6.6 HANDLING OF MISSING DATA AND OUTLIERS

Multiple imputation will be used in the estimation of propensity scores and in multivariable regression analyses. In descriptive analyses, the fraction of missing observations will be reported. Every effort will be made to collect complete data at the specified time points. Any removal from the analysis will be documented, stating the site and patient number as well as the reason for removal.

6.7 BASELINE, TIME WINDOWS AND CALCULATED VISITS

Baseline visit (Visit 1) will include historical and demographic data as well as registration and initial examination.

Treatment with Spiolto® Respimat® will be documented at visit 1 and visit 2, after approximately 12 weeks of treatment.

Proprietary confidential information © 2020 Boehringer Ingelheim International GmbH or one or more of its affiliated companies

The mMRC breathlessness scale as well as the CAT™ questionnaire (health and functional status) is completed by the patient at visit 1 and (after approximately 12 weeks of treatment) visit 2.

In addition, the PGE is completed by the physician at visit 1 and visit 2 as well as satisfaction survey at visit 1 (regarding the preceding therapy) and visit 2 (regarding the new therapy).

7. PLANNED ANALYSIS

The analyses of the primary and secondary endpoints will be performed on the matched set (MS) using the primary analytical approach (propensity score matching).

The primary will further be analysed using propensity score weighting and multivariable regression modeling. These analyses will be performed on the treated set (as-treated analysis) and, additionally, on the per-protocol set (PP).

Additionally, the primary and secondary endpoints will be analysed on the treated set (TS) based on data as collected (i.e. without applying any analytical approach).

The propensity score will be calculated based on a logistic regression model taking the choice of treatment as dependent variable and baseline characteristics as independent variables into account. Further details are given in section 7.3.

7.1 DEMOGRAPHIC AND OTHER BASELINE CHARACTERISTICS

Only descriptive statistics are planned for this section of the report. All baseline analyses will be done for the treated set and the matched set.

For categorical variables summary tabulations of the number and percentage within each category (with a category for missing data) of the parameter will be presented. For continuous variables number of values, mean, standard deviation, minimum, 25th percentile, median, 75th percentile, maximum and number of missing values will be presented. Incidence rates and 95% CI will be given when appropriate. Known right-skewed variables will be log-transformed for computation of means.

7.2 CONCOMITANT DISEASES AND MEDICATION

Only descriptive statistics are planned for this section of the report. All analyses will be done for the treated set.

7.3 PRIMARY ENDPOINTS

The primary outcomes are reported in a descriptive manner, will be compared in an explorative manner and are not safety outcomes. For the three primary outcomes the comparative treatment effect will be estimated along with 95% confidence intervals (CI).

For absolute changes in total mMRC and CATTM score between baseline and end of observation, summary statistics will be provided. Furthermore linear regression will be used to analyse the change in mMRC and CATTM score. The model will adjust for clustering (matched patients) using generalized estimating equations (GEEs) and take the respective baseline variable as covariate into account.

In an additional analysis it will be investigated if the therapy effect is heterogeneous with respect to the GOLD spirometric classification and the GOLD patient group, respectively. The stratified estimators with their corresponding 95% confidence interval will be shown. If

appropriate, a p-value of the interaction of treatment and GOLD may be provided. If some of the strata are too small they will be omitted from the analysis. **mMRC and CAT™ score**

The mMRC Dyspnea Scale consists only of one question on symptom severity and yields a score of either 0, 1, 2, 3 or 4.

The total CAT™ score ranges from 0 to 40. A higher score is indicative of worse status. According to the manual missing values will not be imputed, no total score will be calculated if at least one item is missing. However a single imputation will be done as sensitivity analysis, by imputing the response for the missing question as mean of the other questions of the respective patient.

The total CAT™ score and the corresponding subscales are calculated as follows, in case that answers to all 8 items are available:

$$\text{Total CAT}^{\text{TM}} \text{ score} = \sum_{i=1}^8 \text{item}_i$$

The estimation of the treatment effect is subject to potential confounding. Therefore, beside the analysis based on data as collected adjusted analyses are required. Multiple analytical approaches will be applied to allow an assessment of the sensitivity of the results to these approaches:

- Propensity score matching (primary analysis; requires data to be discarded from the analysis)
- Propensity score weighting (uses the complete data set)
- Multivariable regression modeling (uses the complete data set)

Ten multiple imputations will be applied to estimate the propensity score model and the multivariable regression models. The average of the propensity scores will be used to analyze the treatment effect.

Propensity score matching:

Estimation of propensity scores will be realized via multivariable logistic regression, modelling treatment dependent on several matching variables.

Variables used for propensity score estimation are:

- age at registration [continuous variable]
- age at registration squared [continuous variable]
- sex [male / female]
- baseline CAT™ [continuous variable]
- baseline mMRC [mMRC-grade 0 / mMRC-grade I / mMRC-grade II / mMRC-grade III / mMRC-grade IV]
- exacerbation history [yes: at least 1 exacerbation requiring hospitalization or at least 2 moderate exacerbations / no: no exacerbations or only mild exacerbations]

- pack-years of smoking [continuous variable]
- FEV1 [no finding / < 30% / 30% - 49% / 50% - 79% / ≥ 80%]
- Logarithm of eosinophil levels [continuous variable]
- Specialization of attending physician [GP/ pulmonologist/ internal specialist]

If the propensity score model can be fitted without convergence problems, no further variable selection will be performed. In case of convergence problems, variables causing failed convergence will be eliminated from the model.

Density curves of the propensity score distribution stratified by treatment group will be shown to assess overlap.

Matching based on the propensity score is realized using a (greedy) nearest-neighbor matching on the logit of the propensity score with a caliper of 0.2 standard deviations of the logit of the PS.

Matching of patients treated with Spiolto® Respimat® to patients treated with triple combination (free or fixed LAMA + LABA + ICS) will be implemented using PROC PSMATCH with a random order of treated patients to be matched. It will be started with a 1:1 matching, but if the balance can be kept a 1_{Triple}:2_{Spiolto} or even 1_{Triple}:3_{Spiolto} matching will be performed.

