9.2.2 Study population

Inclusion Criteria:

Patients can be included if all of the following criteria are met:

- Diagnosis of COPD
- Symptomatic (with regard to dyspnea (mMRC Dyspnea score ≥ 1) AND with regard to symptoms (CAT Score ≥ 10) at the same time)
- Patients on LABA/ICS maintenance therapy who are switched to Spiolto[®] Respimat[®] in the new reusable inhaler or a free/fixed triple combination of LABA + LAMA + ICS at Visit 1 at the discretion of the treating physician.
- Adults who are contractually capable and mentally able to understand and follow the instructions of the study personnel
- Male or female
- Patients aged ≥ 40 years of age
- Written informed consent prior to study participation
- The patient is willing and able to follow the procedures outlined in the protocol

Exclusion Criteria:

- Patients with contraindications acc. to SmPC
- Patients not on LABA/ICS maintenance treatment at visit 1, e.g., mono or dual bronchodilation only, ICS only, or a triple combination of LAMA + LABA + ICS (either as a fixed combination product or as separate components)
- Lack of informed consent
- Pregnant and/or lactating females
- Acute exacerbation of COPD (within 4 weeks prior to Visit 1)
- Frequently exacerbating COPD patients, i. e. patients with ≥ 2 moderate exacerbations within the last 12 months or ≥ 1 exacerbation leading to hospitalization within the last 12 monthsⁱⁱⁱ
- Acute respiratory failure (pH $< 7,35$ and/ or respiratory rate $> 30/\text{min}$ within 3 months prior to Visit 1)
- History or current diagnosis of asthma
- History or current diagnosis of asthma-COPD overlap
- History or current diagnosis of allergic rhinitis within the last 5 years

ⁱⁱⁱ Definitions of exacerbation severity according to German Pulmonary Society Guideline (DGP-Leitlinie 2019)⁸

- History or current diagnosis of lung cancer within the last 5 years
- Participation in a parallel interventional clinical trial
- mild exacerbation: additional use of short-acting bronchodilators and treated by the patient without consulting a physician
- moderate exacerbation: treatment includes medical prescription of a systemic corticosteroid and/or antibiotic
- severe exacerbation: exacerbation leading to hospitalization

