9.2.3 Study visits

Patients will be enrolled consecutively and will be followed over an observational period of approximately 12 weeks. Two study visits will be performed.

Patients will be attributed to either group (triple therapy or Spiolto® Respimat®) on the investigator's discretion and patient's consent before study start at visit 1 (Baseline).

If possible and manageable and in compliance with the investigator's decision, a 1:1 group distribution of the patients included per site should be aimed at. However, a strict distribution scheme is not given.

At Visit 1 (baseline), after information and signature of the Informed Consent Form, the patient will be included into the NIS. The patient will of course have enough time for considering study participation.

At Visit 2, after approximately 12 weeks of treatment, the observation of the patient will end. The respective exams and data to be collected are listed in [Table 9.2.3.1](#).

Table 9.2.3.1: Visit flow chart and data collection parameters

| Parameter | Visit 1; baseline visit | Visit 2; approx. 12 weeks after baseline visit |
|--|-------------------------------|---|
| Informed Consent | X | |
| Specialization of attending physician (GP, pulmonologist, internal specialist) | X | |
| Inclusion / Exclusion Criteria | X | |
| Patient demographics (age, gender, height, and weight) | X | |
| History of COPD | X | |
| Rationale for changing COPD maintenance therapy | X | |
| Number and severity of exacerbations in the last 12 months | X | |
| Number of exacerbations leading to hospitalization in the last 12 months | X | |
| Device training (yes/no), reason for no training | X | |

Table 9.2.3.1 (cont'd): Visit flow chart and data collection parameters

| Parameter | Visit 1; baseline visit | Visit 2; approx. 12 weeks after baseline visit |
|--|-------------------------------|---|
| COPD severity based on GOLD assessment ^{iv} (GOLD patient groups) | X | |
| GOLD spirometric classification, if available ^v , incl. date of examination | X | |
| Eosinophils in peripheral blood, if available | X | |
| Smoking history, current status, pack-years | X | |
| Concomitant diseases / Comorbidities | X | X |
| Current COPD related and other relevant concomitant medication | X | X |
| mMRC breathlessness scale, completed by the patient | X | X |
| Health and functional status by CAT TM questionnaire, completed by patient | X | X |

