9.7 DATA ANALYSIS

Details on the statistical analyses will be given in a statistical analysis plan (SAP). In brief, the planned analyses will be conducted as follows:

All patients who have received at least one dose of Spiolto® Respimat® or triple combination (free or fixed LAMA + LABA+ ICS) will be included in the analysis; this is the treated set. All analyses will be performed on the treated set (as-treated analysis).

The analyses will relate to the following data:

- primary outcome: Therapeutic success based on mMRC score difference;
- primary outcome: Therapeutic success based on CAT™ score difference;
- secondary outcome: Changes from Visit1 to Visit 2 in the mMRC and CAT™ scores;
- Specialization of attending physician (GP, pulmonologist, internal specialist)

- Patient demographics (gender, age, height, weight)
- Comorbidities (main diagnosis and concurrent diagnosis according to MedDRA, version valid as at the time of database closure)
- COPD related and other concomitant medication (according to the WHO classification, version valid at the time of database closure)
- History of smoking / current smoking and pack years
- Reported number and severity of exacerbations in the last 12 months
- Dyspnea based on mMRC score at visit 1 and visit 2
- Symptom burden based on CAT™ score at visit 1 and visit 2
- Patient satisfaction with inhaler and therapy at visit 2 only; secondary outcome
- General condition of the patient: evaluated by the physician (Physician's Global Evaluation (PGE)), secondary outcome
- Patient's willingness to continue, reason for unwillingness; secondary outcome
- Adverse Drug Reactions (ADR and SADR), fatal AEs, pregnancies
- GOLD spirometric classifications (1, 2, 3, 4) and GOLD patient groups (A, B, C, D)
- Details of current treatment with inhaled respiratory agents at Visit 1
- Details of treatment with respiratory agents during the study
- Reasons for ending treatment during the observation period
- Details of treatment continuation / discontinuation

Descriptive statistics for comparison of baseline characteristics and crude outcome analyses comprise N / mean / SD / min / median / max for continuous variables, while for categorical variables tabulations of relative and absolute frequencies will be presented. Incidence rates and 95% CI will be given where appropriate.

All analyses will be carried out using SAS® statistical software, version 9.4 or higher (██████████).

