9.7.1 Main analysis

For the two primary outcomes, as specified in section 9.3.2.1, the comparative treatment effect will be estimated along with 95% confidence intervals.

The estimation of the treatment effect is subject to potential confounding. Therefore, adjusted analyses are required. Multiple analytical approaches will be applied to allow an assessment of the sensitivity of the results to these approaches:

- Propensity score matching (primary analysis; requires data to be discarded from the analysis)

[figure not shown]
Proprietary confidential information © 2019 Boehringer Ingelheim International GmbH or one or more of its affiliated companies

- Propensity score weighting (uses the complete data set)
- Multivariable regression modeling (uses the complete data set)

Multiple imputation will be applied to estimate the propensity score model and the multivariable regression models.

Covariates for adjustment include patient demographics (age, sex), disease characteristics (baseline CATTM / mMRC, exacerbation history, pack-years of smoking, FEV₁, eosinophil levels) and health care provider (GP / pulmonologist). Baseline comparability before and after matching will be assessed using standardized differences.

The comparative effectiveness on the primary endpoints will be determined based on model coefficients (along with 95% confidence intervals) and statistical testing of these coefficients. Since the study is exploratory in nature, no multiplicity adjustment is planned.

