6.2 IMPORTANT PROTOCOL DEVIATIONS

Table 6.2: 1 defines the different categories of important protocol violations (PVs). The final column describes which PVs will be used to exclude subjects from the different patient analysis sets^[2].

Table 6.2: 1 Important protocol violations

Category/Code		Description	Requirements	Excluded from
A		Entrance criteria not met		
	A1.1	Inclusion criterion 1 (Diagnosis of COPD)	Not met as specified in the protocol	PP, MS
	A1.2	Inclusion criterion 2 (Symptomatic (with regard to dyspnea (mMRC Dyspnea score ≥ 1) AND with regard to symptoms (CAT Score ≥ 10) at the same time))	Not met as specified in the protocol	PP, MS
	A1.3	Inclusion criterion 3 (Patients on LABA/ICS maintenance therapy who are switched to Spiolto® Respimat® in the new reusable inhaler or a free/fixed triple combination of LABA + LAMA + ICS at Visit 1 at the discretion of the treating physician.)	Not met as specified in the protocol	PP, MS
	A1.4	Inclusion criterion 4 (Adults who are contractually capable and mentally able to understand and follow the instructions of the study personnel)	Not met as specified in the protocol	PP, MS
	A1.5	Inclusion criterion 5 (Male or female aged ≥ 40 years of age)	Not met as specified in the protocol	PP, MS
	A1.6	Inclusion criterion 6 (Written informed consent prior to study participation)	Not met as specified in the protocol	PP, MS
	A1.7	Inclusion criterion 7 (The patient is willing and able to follow the procedures outlined in the protocol)	Not met as specified in the protocol	PP, MS
	A2.1	Exclusion criterion 1 (Patients with contraindications acc. to SmPC)	Met as specified in the protocol	PP, MS
	A2.2	Exclusion criterion 2 (Patients not on LABA/ICS maintenance treatment at visit 1, e.g., mono or dual bronchodilation only, ICS only, or a triple combination of LAMA + LABA + ICS (either as a	Met as specified in the protocol	PP, MS

Category/Code	Description	Requirements	Excluded from
	fixed combination product or as separate components))		
A2.3	Exclusion criterion 4 (Pregnant and/or lactating females)	Met as specified in the protocol	PP, MS
A2.4	Exclusion criterion 5 (Acute exacerbation of COPD (within 4 weeks prior to Visit 1))	Met as specified in the protocol	PP, MS
A2.5	Exclusion criterion 6 (Frequently exacerbating COPD patients, i. e. patients with ≥ 2 moderate exacerbations within the last 12 months or ≥ 1 exacerbation leading to hospitalization within the last 12 months ¹)	Met as specified in the protocol	PP, MS

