6.3 PATIENT SETS ANALYZED

Treated set (TS): All patients with informed consent who have received at least one dose of Spiolto® Respimat® or triple combination (free or fixed LAMA + LABA+ ICS).

[figure not shown]
Per-protocol set (PP): All patients with informed consent who met all inclusion criteria as well as no exclusion criteria and have received at least one dose of Spiolto® Respimat® or triple combination (free or fixed LAMA + LABA+ ICS).

Matched set (MS): Subset of PP excluding all patients who could not be matched in the propensity score matching.

Table 6.3: 1 Patient sets analyzed

Class of endpoint	Patient set		
	TS	PP	MS
Primary	X	X	X
Secondary endpoints	X		X
Safety endpoints	X		
Demographic/baseline	X		X

If the number of patients excluded from the PP is small (<10% of the TS), then analyses on this set may not be conducted.

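### The exacerbation-history covariate in SAP 7.3 separates no eligible patients: its 'yes' level matches an exclusion criterion, and exactly one moderate exacerbation has no level

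*SAP*

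**What the plan says.** Protocol 9.7.1 lists the covariates for adjustment, among them "exacerbation history, pack-years of smoking". It gives no coding; details are left to the SAP.

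SAP 7.3 supplies the coding, in the same words for the propensity score and for the multivariable regression: "exacerbation history [yes: at least 1 exacerbation requiring hospitalization or at least 2 moderate exacerbations / no: no exacerbations or only mild exacerbations". It states no look-back period.

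Protocol 9.2.2 excludes frequent exacerbators, defined as "patients with ≥ 2 moderate exacerbations within the last 12 months or ≥ 1 exacerbation leading to hospitalization" in the same 12 months. It keeps moderate events apart from mild ones: "moderate exacerbation: treatment includes medical prescription of a systemic corticosteroid and/or antibiotic". Mild events are those the patient handles with extra short-acting bronchodilator without seeing a physician. Severe events are those leading to hospitalization.

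SAP 6.2, Table 6.2: 1, code A2.5, carries the exclusion over ("Frequently exacerbating COPD patients, i. e. patients with ≥ 2 moderate exacerbations within the last 12 months", or a hospitalized event) and removes these patients from the per-protocol set (PP) and the matched set (MS). SAP 6.3 defines the latter: "Matched set (MS): Subset of PP excluding all patients who could not be matched in the propensity score matching". SAP 7 runs the primary analysis on MS, and runs weighting and regression on the treated set (TS) and PP.

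The data collected at Visit 1 (Protocol Table 9.2.3.1) are "Number and severity of exacerbations in the last 12 months".

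**The concern.** Treatment is chosen by the physician, so the comparison depends on the covariate adjustment. The protocol itself gives reasons to treat exacerbation history as a confounder. The rationale in its Abstract ties the use of ICS to exacerbations and exacerbation risk, and the arms differ in whether ICS is kept. Section 7.1.1 says that recurrent exacerbations worsen health status, which CAT measures.

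Once frequent exacerbators are excluded, the only moderate-or-severe contrast left among eligible patients is none versus one moderate exacerbation. The SAP's variable does not code that contrast. Two things are at stake:

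- The report could state that the comparison was adjusted for exacerbation history when, among eligible patients, no such adjustment took place.
- One class of eligible patients cannot be coded without a programming decision that the SAP does not record.

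**Working it through.** The plan gives no figure on this point, so the check is mainly a logical one.

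**Step 1. Set the two rules side by side**, with a 12-month look-back for both (see the last step):

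| Moderate events | Hospitalized events | Protocol 9.2.2 | SAP 7.3 level |
|---|---|---|---|
| 0 (mild or none) | 0 | eligible | no |
| exactly 1 | 0 | eligible | none defined |
| 2 or more | 0 | excluded | yes |
| any | 1 or more | excluded | yes |

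Every 'yes' row is an excluded row and the reverse. The row with one moderate event is not 'yes' because the threshold is two. It is not 'no' because that level admits only none or mild, and the protocol defines moderate as a separate class.

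**Step 2. Enumerate as a check.** Take mild absent or present (2), moderate 0 to 4 (5) and hospitalized 0 to 2 (3): 2 × 5 × 3 = 30 histories.

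- Eligible: 2 (mild) × 2 (moderate 0 or 1) × 1 (hospitalized 0) = 4. Of these, 2 are 'no', 2 have no level and 0 are 'yes'.
- Excluded: 30 − 4 = 26, all 'yes'.

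These are counts of combinations, not of patients, and they depend on the grid. The pattern does not: no eligible history is 'yes' on any grid.

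**Step 3. Follow each way of coding the one-moderate patients.**

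- Put into 'no': this contradicts the words of that level, and the covariate is constant in PP and MS.
- Set to missing and imputed among eligible patients: every observed value is 'no', so imputation has no contrast to restore.
- Set to missing and imputed in TS: the only observed 'yes' values come from patients enrolled in violation of the criterion.

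Let q be the share of eligible patients with exactly one moderate exacerbation. A variable that separated them would have variance q(1 − q). For assumed q of 10%, 20%, 30% and 40% this is 0.09, 0.16, 0.21 and 0.24. Under the SAP coding, with these patients in 'no', it is 0.

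**Step 4. Relate this to the SAP's balance limit.** SAP 7.3 treats a standardized difference below 0.1 as negligible. With a the share with one moderate exacerbation in one arm and b the larger share in the other, solve

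(b − a) / √{[a(1 − a) + b(1 − b)] / 2} = 0.1.

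| a (assumed) | b | Difference, points | Of 259 per group |
|---|---|---|---|
| 10% | 13.2% | 3.2 | 8.3 |
| 20% | 24.1% | 4.1 | 10.7 |
| 30% | 34.7% | 4.7 | 12.1 |
| 40% | 44.9% | 4.9 | 12.8 |

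The 259 is the evaluable number per group for CAT in Protocol 9.5.1. The table solves upward from a. Going down from 10%, a share of about 7.2% (2.8 points) also reaches 0.1. Larger gaps behave the same way: assumed shares of 10% versus 20% give (0.20 − 0.10) / √[(0.09 + 0.16) / 2] = 0.28. With one-moderate patients coded 'no', the variable's own standardized difference in PP and MS would show none of this.

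**Step 5. Check the look-back.** The covariate names no window. Protocol Table 9.2.3.1 and section 9.3 list exacerbation number and severity for the last 12 months only, which is also the exclusion window. A longer window could make an eligible patient 'yes', but no such counts are planned.

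**The case against.** **No harm is demonstrated.** The documents do not show that none versus one moderate exacerbation changes the 12-week CAT or mMRC result. The strongest exacerbation contrast is removed by the exclusion. The score still holds baseline CAT and mMRC, FEV1, eosinophils, pack-years and physician specialty, and the study is declared exploratory. It is right that no bias size can be claimed. But SAP 7.3 says adjusted analyses are required because of confounding, and this covariate is one the protocol names.

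**Levels for ineligible patients have a use.** The lists also contain mMRC grade 0, although inclusion requires at least 1, and TS can contain violators. This is fair: an empty level does no damage by itself. The fault is that the covariate offers no other contrast.

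**One moderate event would simply be coded 'no'.** That is the natural guess for a yes/no variable and would close the derivation gap. It conflicts with the text, and the covariate remains constant among eligible patients.

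**Imbalance would be visible anyway.** Protocol 9.7 lists "Reported number and severity of exacerbations in the last 12 months" for analysis, and SAP 7.1 gives baseline tables for TS and MS. A reader may well see an imbalance there. The tables do not adjust for it.

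**A level for violators may be sparse and upset convergence in TS.** This is possible, but the SAP's present 'yes' level is already exactly that group.

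**Conclusion.** The point holds and the definition is wrong as written. Among eligible patients the covariate is 'no', or undefined for those with exactly one moderate exacerbation, and never 'yes'. In TS, 'yes' identifies only patients who violate the exclusion criterion. Neither matching, weighting nor regression therefore adjusts for exacerbation history among eligible patients.

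This rests on one inference, that the covariate uses the 12-month data collected at Visit 1, since the SAP states no window. The share of patients affected and the size and direction of any bias are not known from the documents. The percentages in the working are assumptions that only give scale, and a standardized difference of 0.1 is a balance flag, not an estimate of bias. The change must be made before the analysis, because the defect lies in a named confounder of a non-randomized primary comparison.

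**What to change.** In both covariate lists in SAP 7.3, define exacerbation history over the 12 months before Visit 1 as:

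- no exacerbation or only mild;
- exactly one moderate, none hospitalized;
- in treated-set analyses only, a separate level for ineligible patients (two or more moderate, or any hospitalized). This level is empty in PP and MS.

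Among eligible patients the number of moderate exacerbations can only be 0 or 1, so using that count instead would give the same contrast there.

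State the 12-month look-back. Report the standardized difference for one moderate exacerbation before and after matching. Because SAP 7.3 eliminates variables that cause failed convergence, say that a sparse ineligible level in TS is not a reason to drop the whole variable.

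The cost is SAP wording and a recode. Number and severity of exacerbations are already collected at Visit 1. The models gain one or two parameters, and the ineligible level in TS may be sparse, as the present 'yes' level would be.

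### The only stated remedy for a non-converging propensity model is to delete the whole variable, so one sparse level could remove a pre-specified confounder from both matching and weighting

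*SAP*

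**What the plan says.** Protocol 9.7.1 names the confounders in advance: "Covariates for adjustment include patient demographics (age, sex), disease characteristics" such as baseline CAT and mMRC, exacerbation history, pack-years, FEV1 and eosinophils, plus type of provider. SAP 7.3 turns these into a logistic model. When it fits, the list stands: "If the propensity score model can be fitted without convergence problems, no further variable selection will be performed". When it does not: "In case of convergence problems, variables causing failed convergence will be eliminated from the model". No other remedy, order of steps or later adjustment for a deleted variable is given.

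Two listed variables have levels that an eligible patient cannot occupy:

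- mMRC is coded as "baseline mMRC [mMRC-grade 0 / mMRC-grade I / mMRC-grade II / mMRC-grade III / mMRC-grade IV", while Protocol 9.2.2 requires "mMRC Dyspnea score ≥ 1".
- Exacerbation history is coded as "exacerbation history [yes: at least 1 exacerbation requiring hospitalization or at least 2 moderate exacerbations", which repeats an exclusion criterion in the same protocol section.

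SAP Table 6.2: 1 excludes entry violators from the per-protocol (PP) and matched sets, and SAP 6.3 defines the matched set as a subset of PP. Of weighting and regression, SAP 7 says: "These analyses will be performed on the treated set (as-treated analysis) and, additionally, on the per-protocol set (PP". It does not say on which set the propensity model is fitted.

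**The concern.** A common cause of non-convergence in a logistic model is separation: all patients in some level received the same treatment. The rule then removes every level of that variable, including those where the arms overlap and adjustment works. A variable strongly related to treatment choice is the one most in need of adjustment, and this rule can remove it.

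What is lost is confounding control in an observational comparison whose stated aim (Protocol 7.1.6) is to learn whether switched patients fare no worse than on triple therapy. Weighting uses the same score, so it inherits the deletion and cannot serve as an independent check. The rule also leaves it to the data, after the fact, to decide which of the pre-specified confounders count.

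**Working it through.** **Inputs from the documents.** CAT margin 2 points, SD 7, one-sided alpha 2.5%, power 90%, 10% dropout within a total loss of 40% (Protocol 9.5.1); greedy matching on the logit score with a 0.2 SD caliper, and an outcome model containing the endpoint's own baseline score (SAP 7.3).

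**The plan's own figure.** The SAP gives no figure for this rule. As background, the CAT sample size reproduces: 2 × 7² × (1.960 + 1.282)² / 2² gives 258 per group by the normal approximation and 259 with the t distribution; 259 / 0.6 = 432 per group, 864 in total. After 10% dropout, 864 × 0.9 ≈ 778 patients remain before matching.

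**Chance that a level with k patients lies wholly in one arm.** With share p in one arm it is p^k + (1 − p)^k, if arm is unrelated to level.

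| k | 1:1 | 2:1 |
|---|---|---|
| 2 | 50% | 56% |
| 3 | 25% | 33% |
| 4 | 12.5% | 21% |
| 10 | 0.2% | 1.7% |

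The route is therefore realistic only for very small levels.

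**Effect of dropping mMRC.** Simulation: 778 patients, 150 runs per scenario, true effect 0, matching as in the SAP at 1:1, CAT change adjusted for baseline CAT. Four grade 0 patients (4/778 ≈ 0.5%) were placed in the Spiolto arm. Assumed: odds of Spiolto multiplied by 0.8 or 0.6 per mMRC grade, 1 or 2 CAT points per grade, correlation of 0.3 or 0.6 between baseline CAT and the severity underlying mMRC.

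- With mMRC in five classes the fit failed in every run (criterion: coefficient change below 1e-6 within 25 steps; other software criteria may differ).
- mMRC dropped: absolute standardized difference of mMRC after matching 0.16 to 0.44 (0.22 to 0.47 before); CAT bias 0.15 to 0.71 points, which is 0.15/2 = 7.5% to 0.71/2 = 35.5% of the margin.
- Grade 0 merged with grade I and mMRC kept: absolute standardized difference about 0.01; bias 0.0 to 0.12.
- Monte Carlo error: about 0.5/√150 = 0.04.

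A second simulation with other assumptions (200 data sets per scenario, other covariates explaining 5% to 15% of CAT change, matched mean difference) gave 0.11 to 0.44 points with mMRC dropped and 0.09 to 0.35 with FEV1 dropped. With the full list, bias stayed within about 0.05.

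**What such a bias does to a reading against the margin.** SE = 7 × √(2/259) = 0.615. One-sided error at the margin, for a bias b towards Spiolto, is Φ(b/0.615 − 1.96). Power, for the same bias against it, is Φ((2 − b)/0.615 − 1.96).

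| b | error at margin | power |
|---|---|---|
| 0 | 2.5% | 90% |
| 0.15 | 4.3% | 85% |
| 0.71 | 21% | 55% |

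**The case against.** The strongest case against is that the primary comparison is better protected than the rule alone suggests.

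- A reader might infer that a handful of mMRC grade 0 violators is likely to strip mMRC from the primary analysis. Those patients are barred from PP and from the matched set. If the score is fitted on PP, grade 0 is empty and separates nothing. The route stays open only because the fitting set is unstated and weighting on the treated set needs a score there.
- A reader might expect the FEV1 class below 30% to fail too. The documents give no frequency for it, and at equal allocation ten patients would separate with probability 2 × 0.5^10 = 0.2%.
- Baseline mMRC is not lost for the mMRC endpoint, because the outcome model carries it. That does not help the CAT comparison, nor a deleted FEV1 or specialization for either endpoint.
- Correlated covariates left in the score carry part of a deleted variable.
- Standardized differences and overlap plots may show the damage, and the multivariable regression does not state this deletion rule. But no action follows a standardized difference of 0.1 or more, the SAP does not say that deleted variables are checked, and the regression selects covariates by p-value and is not primary.
- Deleting exacerbation history among eligible patients costs nothing. As coded, only its 'no' level can occur there, so a flat ban on removing any variable could not work.

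These points limit how often and how far the rule can do harm. None makes whole-variable deletion the better remedy.

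**Conclusion.** The point stands as a conditional weakness that should be corrected. The rule is the SAP's only answer to non-convergence, it acts on whole variables, and it affects both propensity-based analyses. If mMRC alone were dropped, the CAT bias would be roughly 0.1 to 0.7 points against a 2-point margin. That range rests entirely on assumed selection and prognostic strength.

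Three stronger readings are not supported. A bias as large as 0.81 points (0.81/2 ≈ 41% of the margin) appears in simulation only with mMRC and FEV1 both deleted under strong selection, a joint event for which the documents give no probability. A bias in favour of Spiolto assumes that milder patients receive it and improve more, which the documents do not state. And non-convergence itself is possible, not predicted. The study also calls itself exploratory, so the error rates above illustrate a reading against the margin used for sample size; they are not properties of a test specified in the SAP.

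**What to change.** Replace the sentence in SAP 7.3 with:

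> The propensity model is fitted separately in each analysis population used (PP for matching; TS and PP for weighting). If it does not converge, sparse or ineligible levels are first merged with the neighbouring level (mMRC 0 with I, FEV1 <30% with 30-49%). If it still fails, Firth-penalised logistic regression is used and the scores are passed to the matching step. A variable is omitted only if it is constant in the fitting set (e.g. exacerbation history as coded, in PP). The same specification is used in all ten imputations. Any listed covariate with a post-matching standardized difference of 0.1 or more is added to the outcome model.

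Specialization and the FEV1 level for no finding have no natural neighbour, so for them the penalised fit is the working step. The line on imputations settles what happens when a variable fails in only some of the ten fits whose scores are averaged.

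The cost is one SAP paragraph and slightly coarser categories; no new data are needed, and the merging and penalised steps change nothing if the model converges. A penalised fit gives finite scores but does not create overlap, so patients in a separating level may remain unmatched, and their number should be reported.
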